5.12. Analysis of Biomarker Variables

Descriptive statistical analyses for the biomarker variables defined in Section 4.12 will be summarized by treatment group and overall for the study, as well as by treatment group and overall within each cohort in the FAS population.

For descriptive summaries, percent change, and/or when appropriate, absolute change from baseline will be provided for biomarker variables at each protocol scheduled time point (as defined by e-CRF visit label) for each treatment group. Missing values will not be imputed.

In addition, all biomarker measurements (scheduled and unscheduled) will be included in patient listing.

6. DATA CONVENTIONS

The following analysis conventions will be used in the statistical analysis.

6.1. Definition of Baseline for Efficacy/Safety Variables

Unless otherwise specified, the baseline assessment is programmatically defined as the last available measurement prior to the date of the first double-blind study treatment administration. For patients randomized and not treated, the baseline value is defined as the last available value prior to the date of randomization.

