10.6. Additional Statistical Data Handling Conventions

The following analysis and data conventions will be followed:

Definition of baseline:

- The baseline assessment will be the latest, valid pre-dose assessment available.

General rules for handling missing data:

- If the start date of an AE or concomitant medication is incomplete or missing, it will be assumed to have occurred on or after the intake of study medication, except if an incomplete date (eg, month and year) clearly indicates that the event started prior to treatment. If the partial date indicates the same month or year of the intake of study medication date, then the start date by the study medication intake date will be imputed; otherwise, the missing day or month by the first day or the first month will be imputed.
- No imputations for missing laboratory data, ECG data, vital signs data, or physical examination data will be made

Visit windows:

- Assessments taken outside of protocol allowable windows will be displayed according to the case report form (CRF) assessment recorded by the investigator

Unscheduled assessments:

- Extra assessments (laboratory data or vital signs associated with nonprotocol clinical visits or obtained in the course of investigating or managing AEs) will be included in listings, but not summaries. If more than 1 laboratory value is available for a given visit, the first observation will be used in summaries and all observations will be presented in listings

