4. ANALYSIS VARIABLES

4.1. Demographic and Baseline Characteristics

For each patient, demographic and baseline characteristics, except TG, will be obtained from the last available value up to the date of the first double-blind study treatment administration (i.e. baseline definition). Baseline TG is defined as the mean of the last 2 measurements during the placebo run-in (day -28, day -14) and week 0. For patients randomized and not treated in R1500-HTG-1522, the baseline value is defined as the last available measurement prior to the date of randomization.

All baseline safety and efficacy parameters (apart from those listed below) will be presented along with the summary statistics in the safety and efficacy sections.

The following variables will be summarized:

Demographic Characteristics

- Sex (Male, Female)
- Race (White, Black or African American, Asian, American Indian or Alaska Native, Native Hawaiian or other Pacific Islander, Not Reported, Other)
- Age in years (quantitative and qualitative variable: ≥ 18 to <45 , ≥ 45 to <65 , and ≥ 65)
- Ethnicity (Hispanic or Latino, Not Hispanic or Latino, Not reported, Unknown)

Baseline Characteristics

- Baseline Weight (kg)
- Baseline Height (cm)
- Baseline Body mass index (BMI) in kg/m^2 (quantitative and qualitative variable defined as <30 , ≥ 30)
- Smoking Status (never, former, and current smoker)
- Current alcohol consumption (yes/no)

Baseline Disease Characteristics

- Lipid parameters - quantitative variables for all efficacy parameters
- HbA1c both quantitative variable and qualitative variable defined as: $<5.7\%$, $\geq 5.7\%$ to $<6.5\%$, $\geq 6.5\%$
- Hs-CRP
- Lp(a): <30 , ≥ 30 to <50 , ≥ 50 mg/dL , and category ≥ 30 mg/dL (<75 , ≥ 75 to <125 , and ≥ 125 nmol/L , and category ≥ 75 nmol/L)
- Cohort assignment
- Patient genotype

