4.7. Efficacy Variables

Efficacy will be assessed through the following measurements:

- **Lipids:** LDL-C (Ultracentrifugation), HDL-C, total-C, fasting TG, non-HDL-C (calculated by subtracting HDL-C from Total-C), Apo B, Apo A1, Apo CIII, Apo B/Apo A1 ratio, and Lp(a)
- **Other variables:** Hemoglobin A1c, hs-CRP, post heparin LPL activity, APOC2, APOA5, and metabolic parameters
- **Imaging:** F-FDG-PET, DW-MRI, and T2-MRI

The baseline value, unless noted otherwise, is defined as the last available measurement prior to the date of the first double-blind study treatment administration (applicable to measurement derivations during both DBTP and SBTP). For patients randomized and not treated, the baseline value is defined as the last available value prior to the date of randomization.

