4.8. Safety Variables

Patient safety will be assessed through the collection of reported adverse events (AEs), clinical laboratory data, vital signs, and ECG. Unless otherwise noted, the baseline value is defined as the last available value before the first dose of double-blind study treatment.

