5.10. Analysis of Anti-evinacumab Antibody Variables

The ADA variables described in Section 4.10 will be summarized using descriptive statistics by dose/cohort group in the ADA analysis set. Listings of ADA positivity and titers presented by patient, time point, and study treatment received will be provided. Incidence of treatment-emergent ADA will be assessed as absolute occurrence (N) and percent of patients (%), grouped by study treatment received.

The influence of ADA on drug concentrations will be evaluated. Assessment of impact of ADA on safety and efficacy may be provided.

Anti-drug antibody status (negative or positive) and titer over the study duration may be classified as follows:

- Negative - negative in the ADA assay at all time points
- Pre-existing immunoreactivity - a positive response in the ADA assay at baseline with all post first double-blind dose results negative in the ADA assay, or a positive response at baseline with all post-first dose responses less than 9-fold of the baseline titer levels

- Treatment emergent response is defined as a positive response in the ADA assay post first double-blind dose when baseline results are negative or missing. The treatment emergent responses will be further characterized as Persistent, Indeterminate or Transient and further categorized as follows:
 - Persistent - Treatment emergent ADA positive response with two or more consecutive ADA positive sampling time points separated by greater than 16-week period (based on nominal sampling time), with no ADA negative samples in between, regardless of any missing samples.
 - Indeterminate - A positive result in the ADA assay at the last collection time point analyzed only, regardless of any missing samples
 - Transient - a treatment emergent ADA positive assay response that is not considered persistent or indeterminate regardless of any missing samples
- Treatment boosted response - defined as a positive response in the ADA assay post first dose, that is at least 9-fold over baseline titer levels when baseline results are positive
- Titer category for subjects, by maximum ADA titer value:
 - Low (titer <1,000)
 - Moderate (1,000≤ titer ≤10,000)
 - High (titer >10,000)
- NAb status (positive or negative)

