10.4.1. Footnotes for the Schedule of Events Table

1. Patients who are permanently withdrawn from study drug before entering the double-blind treatment period (day 1, week 0) will be contacted to assess any AEs.
2. Patients who are permanently withdrawn from the study drug during double-blind period will be asked to return to the clinic for an early termination visit consisting of week 12 study assessments. After the early termination visit, patients will enter the off-drug treatment follow-up period.
3. Patients who are permanently withdrawn from study drug during the single-blind treatment period will be asked to return to the clinic for an early termination visit consisting of week 24 study assessments. After the early termination visit, patients will enter the off-drug treatment follow-up period.
4. Visit 1b must occur at least 4 days after visit 1.
5. Patients will undergo end of double-blind treatment period assessments at the week 12 visit, which is the first visit of administration of single-blind evinacumab.
6. Medical history should include detailed cardiovascular and pancreatitis history.
7. The patient should be fasting for at least 8 hours prior to the post-heparin procedure for measurement of LPL activity. The patient should not consume any alcohol 48 hours prior to the post-heparin plasma blood draw. Heparin (60 U/kg body weight) should be administered IV by bolus injection. Venous blood should be collected 10 minutes after the bolus injection. Prior to discharge from the clinic, patients should then be observed for 1 hour post-heparin administration for any AEs.
8. Following the screening period and confirmation of eligibility, patients will receive an IV bolus of 60 IU of heparin per kg of body weight at visit 2.
9. At dosing visits, all assessments (including urine or serum pregnancy tests for WOCBP) should be performed and all blood samples should be collected before the dose of study drug is administered.
10. Vital signs should also be measured and AEs monitored pre-dose, at the end of study drug infusion, between 30 to 60 minutes post dose, and at approximately 120 minutes post dose. Patients will be closely monitored for a minimum of 120 minutes after IV administration of study drug.
11. Patients should fast for a minimum of 8 hours prior to all blood draws. For patients with diabetes, investigators may hold a patient's morning diabetes medications until labs are drawn and the patient has eaten.

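### SAP 6.1, 4.7 and 4.11 word baseline so that, read literally, day 1 pre-dose samples are excluded; applied to ADA, this would label some pre-existing antibodies as treatment-emergent

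*SAP*

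**What the plan says.** The plan words the general baseline in two incompatible ways.

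**By calendar date, excluding the dosing date.** SAP 6.1, unless otherwise specified: "the baseline assessment is programmatically defined as the last available measurement prior to the date of the first double-blind study treatment administration". SAP 4.7 says of efficacy variables that baseline "is defined as the last available measurement prior to the date of the first double-blind study treatment administration". SAP 4.11 repeats this for the patient-reported outcomes.

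**By order relative to the dose, or including the dosing date.**
- SAP 4.1, for demographic and baseline characteristics other than TG: "last available value up to the date of the first double-blind study treatment administration".
- SAP 4.8, for safety variables: "the baseline value is defined as the last available value before the first dose of double-blind study treatment".
- Protocol 10.6: "The baseline assessment will be the latest, valid pre-dose assessment available".

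TG has its own definition in SAP 4.1, 4.7.2 and 5.7.1, which names week 0 as one of three measurements.

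At dosing visits, footnote 9 to the schedule in SAP 10.4.1 requires that "all blood samples should be collected before the dose of study drug is administered". Protocol 8.2.6.2 says the same for ADA specifically.

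On ADA classification, SAP 5.10 says: "Treatment emergent response is defined as a positive response in the ADA assay post first double-blind dose when baseline results are negative or missing". It also defines pre-existing immunoreactivity and a treatment-boosted response, both of which need a positive baseline result. Protocol 4.4 defines treatment-emergent ADA against a negative pre-dose baseline and does not mention a missing one.

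**The concern.** Day 1 blood is drawn before the infusion but on the same date. A program that keeps only records dated earlier than the first double-blind dose discards those samples, and 6.1 presents itself as the programming rule. For most variables an earlier run-in value remains. For ADA none does, because Amendment 3 moved the baseline sample from visit 3 to day 1.

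The error would also be silent. Since 5.10 lets a missing baseline count as negative, no output fails; patients simply move into the treatment-emergent row. SAP 1.2.2 names treatment-emergent ADA incidence in a secondary objective, so the affected figure is one the study sets out to report.

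**Working it through.** The plan states no figure to reproduce here, so the check is one of logic, followed by a scale calculation under stated assumptions.

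**1. Which samples precede the dosing date?** From the schedules of events (Protocol Table 1; SAP 10.4):

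| Variable | Pre-treatment draws | Literal 6.1/4.7 baseline |
|---|---|---|
| ADA | visit 5 (day 1) only | none |
| Non-TG lipids | visits 3, 4, 5 (after screening) | visit 4, day -14 |
| hs-CRP | visits 3, 5 | visit 3, day -28 |
| TG | own rule: day -28, day -14, week 0 | unchanged |
| Safety laboratory, vital signs, ECG | own rule in 4.8 | unchanged |

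The ADA row marks visits 5, 7, 10 and 13, then end of study. PET is scanned before treatment at visit 4, and MRI uses the mean of two run-in scans (SAP 4.7.5), so neither loses a day 1 value.

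**2. Which rule covers ADA?** SAP 4.10 and 5.10 define no ADA baseline. SAP 4.8 lists adverse events, clinical laboratory data, vital signs and ECG, but not ADA. Within the SAP that leaves 6.1, by default.

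**3. What does 5.10 then do?** Take a patient who is positive on day 1. There are four scheduled post-dose samples (visits 7, 10, 13 and end of study). Each can be negative, positive below 9-fold of the baseline titer, or positive at 9-fold or more. That gives 3^4 = 81 patterns.

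- No sample reaches 9-fold: 2^4 = 16 patterns. At least one does: 81 - 16 = 65.
- Of the 16, one is negative throughout and 15 have at least one positive.

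| True class (day 1 as baseline) | Patterns | Class with baseline missing |
|---|---|---|
| Boosted | 65 | treatment-emergent |
| Pre-existing, some later positive | 15 | treatment-emergent |
| Pre-existing, all later negative | 1 | not treatment-emergent |

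With day 1 as baseline, none of the 81 patterns is treatment-emergent. With baseline missing, 65 + 15 = 80 are. These are counts of patterns, not probabilities.

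**4. Scale.** The expected number misclassified is N × p × r. N = 50 is the planned maximum. The prevalence of pre-existing ADA, p, and the share positive again after dosing, r, are assumptions. The chance of at least one such patient is 1 - (1 - p × r)^50.

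| p | r = 1 | chance of at least one | r = 0.5 | chance of at least one |
|---|---|---|---|---|
| 1% | 50 × 0.01 = 0.5 | 40% | 0.25 | 22% |
| 5% | 50 × 0.05 = 2.5 | 92% | 1.25 | 72% |
| 10% | 50 × 0.10 = 5.0 | 99.5% | 2.5 | 92% |

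One misclassified patient among 50 moves the overall incidence by 1/50 = 2 percentage points.

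**The case against.** The best reply is that nobody intended this. The heading of 6.1 covers efficacy and safety variables, whereas ADA has its own sections; if ADA is treated as safety, 4.8 governs and keeps day 1. Protocol 4.4 speaks of a pre-dose baseline, and the boosted and pre-existing categories of 5.10 make sense only if the day 1 result is used. SAP 1.2.4 lists a changed TG baseline but no departure from Protocol 10.6. The study is exploratory, ADA is summarized descriptively, and listings of titers by patient and time point would still show the day 1 results.

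Most of that stands. The intent was very probably to use day 1, and the harm arises only if 6.1 is applied to ADA as written. It does not remove the conflict: the SAP contains no sentence that gives ADA another baseline. Although 5.10 makes the full classification optional, it commits to reporting treatment-emergent incidence.

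A reader might also infer three stronger claims that the documents do not support.
- *Every pre-existing positive becomes treatment-emergent.* A post-dose positive is still required, so a patient positive on day 1 and negative afterwards is not counted.
- *Day 1 samples are lost across the board.* TG, safety variables, and demographic and baseline characteristics keep them under their own rules.
- *Ultracentrifugation sub-fractions and APOC2, APOC3, APOA5 and NEFA have no baseline either.* In the extracted text, the first draw for these rows falls at visit 4 in the protocol schedule and visit 5 in the SAP schedule. Column positions in extracted tables are not reliable enough to carry the point.

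**Conclusion.** The concern holds in conditional form. The wording of SAP 6.1, 4.7 and 4.11 conflicts with SAP 4.1, SAP 4.8 and Protocol 10.6. If 6.1 is programmed literally and applied to ADA, the ADA baseline is missing for every patient sampled on schedule. Treatment-emergent ADA is then overstated by the number of patients positive both on day 1 and at least once afterwards.

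That number cannot be obtained from the documents. Under the assumed prevalences it is at most about 0.5 to 5 of 50 patients. Non-TG lipids and hs-CRP would still have an untreated run-in baseline, only an older one. The primary analysis is not touched. The point merits correction because a written rule gives a wrong result for a secondary objective, and putting it right costs almost nothing.

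**What to change.** - In SAP 4.7, 4.11 and 6.1, replace the calendar-date cut-off with: *the last available valid measurement taken before the first double-blind dose, including day 1 pre-dose values, ordered by date and time, or by the visit 5 label where the time is missing*. Align 4.1 and 4.8 to the same words, leaving the TG and MRI definitions as they are. For 4.11 the change is for consistency; no loss of diary data has been shown.
- In SAP 5.10, state that the ADA baseline is the day 1 pre-dose sample.
- In SAP 5.10, report patients whose ADA baseline is truly missing separately, because Protocol 4.4 requires a negative pre-dose baseline. If they are still to be counted as treatment-emergent, justify this and add it to the list of modifications in SAP 1.2.4.

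The cost is a few sentences in the SAP and one condition in the derivation program. SAP 6.3 says the date and time of each administration are already recorded in the e-CRF, so no new data are needed. The change should be made before the first database lock at which ADA is analyzed.

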6.2. Definition of Cohort Assignment

Cohort assignment (1,2, and 3) as defined at the time of the analysis will be used for all statistical analyses.

6.3. Data Handling Convention for Missing Data

Missing data will not be imputed in listings. This section includes the methods for missing data imputation for some summary analyses, if necessary.

Date and Time of First/Last Study Treatment

Since the study drug is administered at the site, the date and time of study drug administration are filled in e-CRF. No missing data is expected. Date of first/last administration is the first/last start date of study drug filled in e-CRF.

Adverse Event

If the intensity of a TEAE is missing, it will be classified as “severe” in the frequency tables by intensity of TEAEs. If the assessment of relationship of a TEAE to the investigational product is missing, it will be classified as related to the investigational product.

When the partial AE date/time information does not indicate that the AE started prior to study treatment or after the TEAE period, the AE will be classified as treatment-emergent.

Medication/Procedure

No imputation of medication/procedure start/end dates or times will be performed. If a medication date or time is missing or partially missing and it cannot be determined whether it was taken prior or concomitantly or stopped prior to the first study treatment administration, it will be considered as concomitant medication/procedure.

Potentially Clinically Significant Value (PCSV)

If a patient has a missing baseline value, this patient will be grouped in the category “normal/missing at baseline.”

For PCSVs with 2 conditions, one based on a change from baseline value and the other on a threshold value or a normal range, with the first condition being missing, the PCSV will be based only on the second condition.

For a PCSV defined on a threshold and/or a normal range, this PCSV will be derived using this threshold if the normal range is missing; e.g., for eosinophils the PCSV is >0.5 giga/L or $>\text{ULN}$ if $\text{ULN} \geq 0.5$ giga/L. When ULN is missing, the value 0.5 should be used.

Measurements flagged as invalid by the laboratory will not be summarized or taken into account in the computation of PCSVs.

6.4. Unscheduled Assessments

For efficacy, safety laboratory data, vital signs, ECG, unscheduled visit measurements may be used to provide a measurement for a time point, including baseline, if appropriate according to their definitions. The measurements may also be used to determine abnormal values, AESIs, and PCSVs.

6.5. Statistical Technical Issues

Not Applicable.

7. TIMING OF STATISTICAL ANALYSES

The analyses will be conducted in 2 steps:

- First step: Main Efficacy and Safety Analysis

The first analysis will be conducted when all enrolled patients have completed the double-blind period. This will consist of the final analysis of the primary and secondary endpoints up to week 12. The safety analysis will be performed on all safety data collected and validated at the time of the first analysis.

- Second-step: Final Efficacy and Safety analysis

The second analysis will be conducted at the end of the study and will consist of the final analysis of week 44 efficacy endpoints and final safety analysis

Interim Analyses

Interim analyses may be conducted during the course of the study by the unblinded team to assess efficacy, safety, and futility. If the timing of this analysis falls within a few weeks of the first-step analysis, only the first-step analysis will be performed. Enrollment (up to a maximum of approximately 50 patients) may be halted if the incidence of pancreatitis is much lower than anticipated, making the evaluation of a treatment effect on pancreatitis futile. The following interim analysis is planned:

- The interim analysis will be conducted when the first 9 randomized patients have been administered study treatment in cohort 1 and have completed the double-blind period (i.e., week 12 visit). This will consist of the final data contributing to the analysis of the applicable variables up to week 12 for these 9 patients. In general, interim analysis will include only limited number of outputs applicable for the small sample size. For lipid variables, only descriptive summaries (without within-patient tests) in conventional units will be provided. Other variables (defined in Section 4.7.3) biomarkers, ECG, and PRO variables will not be included. Imaging and PK/ADA may be included in the analyses depending on the availability. For general labs and vital signs only PCSV summary tables will be included. The safety analysis will be performed for these 9 patients on all safety data collected and validated at the time of the first interim analysis. The interim analysis results will be used for the future program development.

The results of the interim analyses will not be used to change the conduct of the ongoing study in any aspect. Individuals involved in the interim analysis of the study will not be involved in the conduct of the study afterwards; individual patient identification will not be released to anyone who is directly involved in the conduct of the study. The interim analysis processes, the measures used to protect the blind and the integrity of the study, the communication plan, and the confidentiality agreement will be described in separate documents.

Additional interim analyses may be conducted if decided by the study team.

Analyses methods and conventions described in the other sections of this SAP will be applied for all analyses as applicable. The following additional rules will apply for analyses performed at interim and first step analyses:

- Patients without end of treatment visit performed at the time of the cut-off date will be considered as ongoing and exposed up to the cut-off date. Therefore:
 - Patients who did not complete the respective treatment period nor prematurely discontinued the study treatment at cut-off date will be analyzed as “ongoing” in the disposition summary.
 - Their TEAE period and treatment period will end at the cut-off date.
 - Their treatment duration will be derived by considering date of cut-off as last administration date.
- Analyses of number of administrations, and mean administration frequency will be performed up to the last administration reported in the e-CRF up to the cut-off date.
- AEs occurring, worsening or becoming serious after the cut-off date will not be included in the analyses. However, any available outcome before database lock, regardless of timing in relation to the cut-off date, of an adverse event starting prior to the cut-off date will be taken into account. Medications, treatment discontinuations/completions and deaths occurring after the cut-off date will not be included in the analyses.
- Post-treatment period, and post-study period are not applicable for ongoing patients. Analyses of post-treatment AEs, post-study deaths and post-treatment medications will be performed for patients who either completed or prematurely discontinued the treatment before or at the cut-off date.
- Analysis of status at last study contact and proportion of patients with insufficient follow-up will be provided for patients who either completed or prematurely discontinued the treatment before or at the cut-off date.

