Efficacy and safety procedures and completion of the pancreatitis daily symptom questionnaire and symptom/dietary impact questionnaire will be performed as outlined in the schedule of events. Imaging correlates of pancreatic health will be assessed by ¹⁸F-FDG PET, by DW-MRI, and by T2-MRI.

Serum samples for the determination of total evinacumab, total ANGPTL3, and anti-drug (anti-evinacumab) antibodies (ADA) will be collected.

Serum and plasma samples will be collected for analysis of additional biomarkers, including amylase and lipase.

Single-Blind Treatment Period (Day 86 to Day 169)

All patients who complete the double-blind treatment period will receive evinacumab administered IV at a dose of 15 mg/kg every 4 weeks (± 4 days) on days 85, 113, and 141.

Stable doses of other triglyceride-lowering therapies, such as fibrates, statins, omega-3s, and niacin are allowed during the study. Glybera[®], mipomersen, or lomitapide are prohibited during the study.

Efficacy and safety procedures and completion of the pancreatitis daily symptom questionnaire and symptom/dietary impact questionnaire will be performed as outlined in the schedule of events. Patients should fast for a minimum of 8 hours prior to any blood draws. Imaging correlates of pancreatic health will be assessed by DW-MRI.

Serum samples for the determination of total evinacumab, total ANGPTL3, and anti-drug (anti-evinacumab) antibodies (ADA) will be collected.

Serum and plasma samples will be collected for analysis of additional biomarkers, including amylase and lipase.

Off-Drug Treatment Follow-up Period (Day 170 to Day 309 [End-of-Study])

Efficacy and safety procedures will be performed as outlined in the Schedule of Events.

Throughout the Study

Patients will be reminded at visits and during phone calls to adhere to a highly effective birth control method. Pregnancy status of female patients of childbearing potential and of female partners (of child-bearing potential) of male patients will be monitored throughout the study and for 24 weeks post the last dose of study drug.

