4.6. Study Treatment Exposure and Compliance Variables

Study treatment exposure variables for infusions administered during the DBTP are listed below with associated definitions:

- Patient duration of double-blind study treatment exposure in weeks defined as: (last double-blind study treatment administration date +28 – first double-blind study treatment administration date)/7, regardless of unplanned intermittent discontinuations. Values will be rounded to one decimal place.
- The total number of double-blind study treatment infusions by patient.
- The following categories will be used for treatment exposure intervals: ≥ 1 day and <4 weeks, ≥ 4 weeks and <8 weeks, ≥ 8 weeks and <12 weeks, ≥ 12 weeks

Study treatment exposure variables for infusions administered during the SBTP are listed below with associated definitions:

- Patient duration of single-blind study treatment exposure in weeks defined as: (last single-blind evinacumab treatment administration date +28 – first single-blind evinacumab treatment administration date)/7, regardless of unplanned intermittent discontinuations. Values will be rounded to one decimal place.
- The total number of single-blind evinacumab treatment infusions by patient.
- The following categories will be used for treatment exposure intervals: ≥ 1 day and <4 weeks, ≥ 4 weeks and <8 weeks, ≥ 8 weeks and <12 weeks, ≥ 12 weeks

Study treatment exposure variables combining DBTP and SBTP are listed below for all patients who received evinacumab in the DBTP:

- Cumulative patient duration of evinacumab exposure in weeks defined as: double-blind treatment exposure plus single-blind treatment exposure, regardless of unplanned intermittent discontinuations.
- Cumulative total number of evinacumab treatment infusions by patient defined as: total number of double-blind infusions plus total number of single-blind infusions.
- The following categories will be used for cumulative patient treatment exposure intervals: ≥ 1 day and <4 weeks, ≥ 4 weeks and <8 weeks, ≥ 8 weeks and <12 weeks, ≥ 12 weeks and <16 weeks, ≥ 16 weeks and <20 weeks, ≥ 20 weeks and <24 weeks, ≥ 24 weeks

With respect to patient treatment administration compliance, the study treatment is administered during the investigative site visits and therefore study compliance will be assessed by infusion frequency for respective treatment periods, specifically:

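### For ongoing patients at the interim and first-step cut-offs, the SAP's exposure rule as written counts 28 days beyond the cut-off in single-blind and cumulative duration

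*SAP*

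**What the plan says.** SAP Section 4.6 defines exposure in weeks separately for each treatment period. The double-blind formula starts from "last double-blind study treatment administration date +28" and the single-blind formula from "last single-blind evinacumab treatment administration date +28". Each then subtracts the first administration date of that period and divides by 7. For patients who received evinacumab in the double-blind period, cumulative exposure is "double-blind treatment exposure plus single-blind treatment exposure, regardless of unplanned intermittent discontinuations". All three durations are also tabulated in four-week categories. The top category is 12 weeks or more for each period and 24 weeks or more for the cumulative figure.

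SAP Section 7 adds rules for the interim and first-step analyses. A patient with no end-of-treatment visit by the cut-off "will be considered as ongoing and exposed up to the cut-off date". Three consequences are listed. One concerns the disposition table. The second reads "Their TEAE period and treatment period will end at the cut-off date". The third reads "Their treatment duration will be derived by considering date of cut-off as last administration date". The paragraph that introduces these rules also states: "Analyses methods and conventions described in the other sections of this SAP will be applied for all analyses as applicable".

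**The concern.** The Section 7 rule replaces one term of the Section 4.6 formula, the last administration date. The 28 days, one dosing interval, are added to exactly that term. They make sense after a real infusion, because they credit the interval that the infusion covers. Added to a cut-off date, they credit four weeks that have not been observed. The same set of rules ends exposure and the treatment period on the cut-off date, so the duration formula disagrees with the sentences next to it.

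At stake are the exposure tables that accompany the first-step safety results. They would show patients part-way through single-blind treatment with as much exposure as patients who finished it, or more.

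**Working it through.** **Inputs.** Single-blind evinacumab is given "every 4 weeks (± 4 days) on days 85, 113, and 141" (Protocol Section 5.1). Double-blind doses fall on days 1, 29 and 57 (same section). The single-blind period lasts 12 weeks (SAP Section 2.3). All figures below use nominal days.

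**Step 1: the formula on completed periods.** Duration = (last dose + 28 − first dose)/7.
- Double-blind: (57 + 28 − 1)/7 = 84/7 = 12.0 weeks.
- Single-blind: (141 + 28 − 85)/7 = 84/7 = 12.0 weeks.
- Cumulative: 12.0 + 12.0 = 24.0 weeks.

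The formula returns the planned period lengths, so the 28 days already account for the interval after the last infusion.

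**Step 2: ongoing single-blind patients, with cut-off on day c.** Three quantities are compared:
- Literal rule: (c + 28 − 85)/7.
- Exposure to the cut-off: (c − 85)/7.
- Actual last dose + 28: (last dose + 28 − 85)/7.

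| Cut-off day | Last dose day | Literal rule (weeks) | To the cut-off (weeks) | Last dose + 28 (weeks) |
|---|---|---|---|---|
| 90 | 85 | 33/7 = 4.7 | 5/7 = 0.7 | 28/7 = 4.0 |
| 127 | 113 | 70/7 = 10.0 | 42/7 = 6.0 | 56/7 = 8.0 |
| 141 | 141 | 84/7 = 12.0 | 56/7 = 8.0 | 84/7 = 12.0 |
| 168 | 141 | 111/7 = 15.9 | 83/7 = 11.9 | 84/7 = 12.0 |

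**Step 3: size against each comparator.**
- Against exposure to the cut-off, the excess is 28/7 = 4.0 weeks for every ongoing patient.
- Against actual last dose + 28, the excess is the time from last dose to cut-off. On the nominal schedule that is 0 to 27 days, or 0 to 3.9 weeks, with a mean of 1.9 weeks if cut-offs fall evenly over days 85 to 168. Visit windows can stretch it. Two doses 28 + 4 + 4 = 36 days apart give about 36/7 = 5.1 weeks. A dose on day 137 with the end-of-treatment visit on day 174 gives 37/7 = 5.3 weeks.

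**Step 4: categories and cumulative exposure.** Measured to the cut-off, the extra 4.0 weeks move an ongoing patient up one four-week category. At day 141 that means the 12-weeks-or-more category with 8.0 weeks elapsed. In the evinacumab arm, cumulative exposure at day 141 is 12.0 + 12.0 = 24.0 weeks, the top category, when (141 − 1)/7 = 20.0 weeks have elapsed. From day 142 the literal single-blind duration exceeds 12.0 weeks, which is more than a completer receives. Measured against actual last dose + 28, the nominal values are 4.0, 8.0 or 12.0 weeks and the literal value stays in the same category. The misplacement is therefore relative to exposure ending at the cut-off, which is the end point Section 7 states.

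**The case against.** The strongest reply is that Section 7 never says the 28 days stay. The duration rule is presented as a consequence of exposure ending at the cut-off, and conventions from other sections carry over only where applicable. A sensible programmer might stop at the cut-off, and the authors may have meant that. This stands as a guess at intent, but not as a reading of the instruction. The rule names the cut-off as the last administration date, which is the very term that Section 4.6 extends by 28 days, and no sentence removes the extension.

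The reply is right to narrow the scope. A reader might infer three larger problems that the documents do not support.

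- **Double-blind exposure inflated at the planned analyses.** Putting day 85 into the formula gives (85 + 28 − 1)/7 = 16.0 weeks instead of 12.0. The first step, however, waits until all enrolled patients have completed the double-blind period, and the planned cohort 1 interim covers nine patients who have completed it. Their actual last dose applies, giving 12.0 weeks. Only an additional interim, which Section 7 permits, could catch patients still in that period.
- **Most patients affected at the first step.** The documents give no accrual rate. If accrual were even over T weeks, with no dropout, roughly 12/T of patients would be within their 12 single-blind weeks when the last patient reaches week 12. That is 50% for T = 24, 23% for T = 52 and 12% for T = 104. These values of T are assumptions. Earlier patients would already be in follow-up.
- **Adverse event results distorted.** SAP Sections 5.8.1, 5.8.3 and 5.8.4 use patient counts and percentages of the safety set, and no exposure-adjusted rate is planned. Section 5.8.2 divides infusion reactions by administrations, which Section 7 counts from actual recorded doses. The treatment-emergent period does end at the cut-off. Completion under Section 4.5 also requires the week 12 or week 24 visit to have been performed, so an inflated duration cannot by itself create a completer.

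**Conclusion.** The point holds as a minor but real error in the written rule. Taken literally, SAP Sections 4.6 and 7 together give values that cannot be right, such as 15.9 weeks in a 12-week period, and they contradict Section 7's own end of exposure. The size is 4.0 weeks per ongoing patient against exposure to the cut-off, or 0 to 3.9 weeks against actual last dose + 28 on the nominal schedule.

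The effect is confined to single-blind and cumulative exposure summaries, with their categories, at the interim and first-step analyses. It extends to double-blind duration only under the additional-interim condition above. Dosing frequency and the primary triglyceride analysis do not use the rule. The second-step analysis takes place at the end of the study with actual last-dose dates, so the error does not persist.

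The conclusion rests on two assumptions: that the 28 days carry over because nothing removes them, and that some patients are still in single-blind treatment at the cut-off. How many there would be cannot be determined from the documents.

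**What to change.** Replace the duration rule for ongoing patients in SAP Section 7 with a statement that, in the period in which the patient is ongoing, duration = (cut-off date − first administration date)/7, without the 28 days. An alternative is (min[cut-off date, last administration date + 28 days] − first administration date)/7. The two agree for patients on schedule. The second stops earlier when a dose is overdue by the cut-off, so the SAP should choose one. Periods already completed keep actual last dose + 28, and cumulative exposure is the sum of the two period durations as now.

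The cost is one sentence of SAP text and one line of programming. No visit, data collection or treatment changes.
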